Because the liver is the primary site of action for the safety and efficacy of OCA, it is important to account for the differences in systemic and liver exposure when assessing effective doses. It is also important to note that while hepatically-impaired (Child-Pugh B and C) subjects treated with OCA in phase 1 and 2 studies experienced plasma OCA exposures >10-fold higher than those in healthy subjects, no apparent impact on the overall safety profile was observed, consistent with only a modest increase in liver exposure of OCA associated with hepatic impairment. Collectively, the results from these analyses suggest that the doses of OCA administered to hepatically-impaired patients should be modestly lower than those for patients with normal hepatic function to achieve similar hepatic exposure.

Per the approved FDA prescribing label, the recommended dosing regimen for OCA in subjects with moderate and severe hepatic impairment is a starting dose of 5-mg OCA once weekly. Dosage adjustments in subjects with moderate (Child-Pugh B) or severe (Child-Pugh C) hepatic impairment may be made after establishing tolerability at the lower dose (full modified dosing regimen is described in [Appendix A](#)).

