- ^k Endoscopy will be conducted at selected study sites where the device is available to assess for the presence of oesophageal varix/varices. Please refer to [Section 9.7.7](#) for additional information related to the allowed window at Day 0 for this specific procedure.
- ^l Ultrasound will be conducted to enhance HCC surveillance. For all on study (eg, post-Day 0) ultrasounds: If a lesion is found, a second confirmatory image (eg, MRI) should be obtained to confirm if a study endpoint has been met.
- ^m Health Outcome Assessments: Data related to non-study related medical or surgical treatment procedures that the subject underwent and any medically relevant health care provider (HCP) or non-HCP related office visits that the subject attended should be collected throughout the study.
- ⁿ Pre-titration tolerability assessment, which include a review of AEs and a review of safety laboratory results (eg, chemistry, hematology, and coagulation), must be completed by the Investigator before any up-titration can occur as defined in [Section 7.4.1](#). Lab results obtained within 2 months prior to any up-titration may be used for assessment.
- ^o Dose Titration is based on cirrhosis status ([Section 9.7.3](#)) and Child-Pugh Score ([Section 9.7.4](#)). The initial dose titration of investigational product may occur at the Month 3 visit, or any study visit thereafter for subjects on all dosing regimens, based on tolerability. Subsequent dose titration(s) for subjects who are classified as Child-Pugh B or Child-Pugh C and following a modified dosing schedule may occur no earlier than 6 weeks after the previous dose titration. For complete modified dose titration criteria, refer to [Appendix A](#).
- ^p Subjects will be instructed to begin dosing on the day after the Day 0 visit (ie, on Day 1) and to take investigational product at approximately the same time of day. Subjects must be instructed to swallow the tablet whole; they must not chew, divide, or crush the tablet.
- ^q The subject should be instructed to fast overnight (at least 8 hours) prior to each visit. Fasting is required prior to all study visits (except Screening Visit 1) but water is permitted.

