7.4.1. Pre-Titration Tolerability Assessment Requirements

Tolerability of investigational product must be assessed prior to titrating a subject to a higher dose. A review of adverse events and safety laboratory results (eg, chemistry, hematology, and coagulation) obtained within 2 months of the up-titration visit must be performed as part of the investigational product tolerability assessment, prior to any planned up-titration in study medication (eg, Month 3, Month 6). Safety laboratory results obtained at the Month 1 visit (for titration at Month 3) or at the 1 Month Post-Titration Assessment visit (for titration prior to or at the subsequent quarterly visit) are acceptable for review purposes; however, if for any reason, laboratory results are not available at the time of the planned up-titration visit, additional laboratory samples must be obtained and reviewed, prior to up-titrating the subject to a higher dose.

To be eligible for a dose up-titration:

- Subjects should not be experiencing significant AEs that are suspected to be related to investigational product (eg, severe pruritus) or displaying other symptoms that may indicate intolerability of investigational product.
- There must be no clinically significant increase (as determined by the investigator) in the subject's liver function tests. Subjects whose total bilirubin is $>2\times$ baseline (and $>ULN$) cannot be up-titrated, and additional unscheduled safety visit procedures, outlined in [Section 9.7.19](#), should be implemented, as required.

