following review of the pre-titration laboratory results to assess safety and tolerability, the dosing frequency of 5 mg OCA or matching placebo should be increased to twice weekly (at least 3 days apart). Subjects who have maintained the twice weekly dosing frequency for a minimum of at least 6 weeks, and meet the dose titration criteria, should up-titrate to twice weekly dosing with 10 mg OCA or matching placebo. Subjects with at least 6 weeks of twice weekly dosing at 10 mg OCA or matching placebo, and meeting dose titration criteria, should up-titrate to the maximum allowed dose of 5 mg OCA or matching placebo once daily.

Investigators may decrease the dosing frequency (back to once or twice weekly) or dose for any subject at any time during the study, as considered clinically appropriate (eg, tolerability).

Modified Dosing Regimen for Subjects with Child-Pugh C Hepatic Impairment

Subjects with cirrhosis and classified as Child-Pugh C at Screening will follow a modified dosing schedule receiving 5 mg OCA or matching placebo once weekly as described in [Figure 2](#). After a minimum of 3 months dosing once weekly with 5 mg OCA or matching placebo, and following review of the pre-titration laboratory results to assess safety and tolerability, the dosing frequency of 5 mg OCA or matching placebo should be increased to twice weekly (at least three days apart). Subjects who have maintained the twice weekly dosing frequency for a minimum of at least 6 weeks, and meet the dose titration criteria, should up-titrate to the maximum allowed dose of 10 mg OCA or matching placebo twice weekly.

Investigators may decrease the dosing frequency (back to once weekly) or dose for any subject at any time during the study, as considered clinically appropriate (eg, tolerability).

Dose Titration due to Change in Cirrhosis or Child-Pugh Score

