Subjects on a modified dosing regimen who demonstrate a change in cirrhosis status and/or Child-Pugh Score should have their dose of investigational product modified to match their current status per the appropriate dosing regimen (see Section 7.4, [Table 5](#)); however, changes to the dosing regimen are not mandatory and should be based on clinical judgment as well as changes in status. Changes in Child-Pugh Score that result from a transient, explainable change in laboratory parameters should be documented appropriately, and should not necessarily result in a change to the dosing regimen. Investigators may contact the medical monitor at any time to discuss potential changes to dosing.

Possible scenarios for dosing modifications include:

- Subjects who develop cirrhosis during the course of the trial with a classification of Child-Pugh B or C
- Subjects with pre-existing cirrhosis who demonstrate a change in the Child-Pugh Score from A to B or C at any point in the study
- Improvement in classification of Child-Pugh Score from C to B
- Improvement in classification of Child-Pugh Score from B to A; these subjects may be eligible to transition to the standard dosing regimen

Subjects may titrate dose and dosing frequency up or down as appropriate, within the appropriate dosing regimen. Up-titration should be done per Investigator discretion and be guided by the pre-titration tolerability assessments outlined in [Section 7.4.1](#). A 1-Month Post-Titration

Assessment must be performed any time a subject's dose or frequency is up-titrated (see [Section 7.1.2](#) and [Section 9.7.10](#)).

Unscheduled Titration Visit, Optional Visit

An unscheduled up-titration visit may be scheduled for as early as 6 weeks after the initial titration visit (or subsequent titration visit) occurs for subjects who are following the modified dosing regimen. The visit procedures required for the unscheduled titration visit are outlined below. Subjects who up titrate at an unscheduled visit will continue to follow the regular visit schedule for all other study visits.

For subjects who up titrate at an unscheduled visit the following procedures will be performed:

- Assess and record AEs.
- Review and record concomitant medications.
- Perform the pre-Titration Tolerability Assessment as outlined in [Section 7.4.1](#).
- Assess the subject's supply of investigational product to ensure an adequate amount. Access the IWRS and dispense investigational product if necessary.

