- Provide the subject with a dosing diary to document his or her dosing.
- Schedule the next visit, reiterate dosing instructions, and advise the subject:
 - NOT to take investigational product on the morning of the next visit, and
 - To bring the investigational product bottle(s); s/he will dose at the clinic (if this is in compliance with the established dosing frequency), and
 - To fast overnight (at least 8 hours) prior to the next visit. Fasting is required prior to all study visits, but water is permitted.

For subjects who up titrate at an unscheduled visit: The + 1-week window week related to the 1-Month Post-Titration visit can be extended for up to an additional 5 weeks to allow for the post-titration assessment to be performed during one of the subject's regularly scheduled study visits. If the window is extended past +1 week allowed visit window, at a minimum, a telephone safety contact should then be performed 1-month post-titration.

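### Modified regimen: up-titration may rest on laboratory results from an earlier, lower dose, so Child-Pugh B subjects can reach Titration 3 with no reviewed chemistry on the dose being left

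*Protocol*

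**What the plan says.** **Age of results.** Table 1 footnote n and Table 2 footnote m in Section 7.1.2 both say: "Lab results obtained within 2 months prior to any up-titration may be used for assessment". Section 7.4.1 repeats the 2-month limit. It adds that results "at the 1 Month Post-Titration Assessment visit (for titration prior to or at the subsequent quarterly visit) are acceptable for review purposes", and that "if for any reason, laboratory results are not available at the time of the planned up-titration visit, additional laboratory samples must be obtained" and reviewed first. It also prohibits up-titration when total bilirubin is above 2x baseline and above ULN.

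**Spacing of steps.** After Titration 1 (Month 3 or later), modified-regimen titrations may follow at intervals of 6 weeks or more (Section 7.3 Table 3, Section 7.4, Appendix A). For the last Child-Pugh B step, Appendix A says: "Subjects with at least 6 weeks of twice weekly dosing at 10 mg OCA or matching placebo, and meeting dose titration criteria, should up-titrate" to 5 mg daily.

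**Post-titration check.** Table 1 footnote b and Appendix A make a laboratory visit mandatory 1 month (+1 week) after every modified-regimen up-titration. After an up-titration at an unscheduled visit, Appendix A relaxes this. The window "can be extended for up to an additional 5 weeks to allow for the post-titration assessment" to coincide with a regular visit, in which case "at a minimum, a telephone safety contact should then be performed 1-month post-titration". The procedures listed for the unscheduled titration visit contain no routine blood draw of their own, only the Section 7.4.1 assessment.

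**Stated principle.** Section 5.5.2.2 says that dose adjustments in moderate or severe "hepatic impairment may be made after establishing tolerability at the lower dose".

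**The concern.** The look-back for laboratory results is longer than the shortest interval between dose steps, and no condition ties the results to the dose being escalated from. A sample can therefore be in date and yet describe an earlier, lower dose.

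The mandatory 1-month check would normally prevent this, but the Appendix A extension removes it in the one place where it is needed. For Child-Pugh B, Titration 2 may be unscheduled, its check may be deferred, and Titration 3 may fall due before that check or on the same day. A bilirubin rise that began on 10 mg twice weekly would then not stop the move to 5 mg daily, because the sample under review predates it. Adverse event review and the telephone call remain, but neither detects an asymptomatic bilirubin rise.

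The Protocol's own model (Section 5.5.2.2) predicts 8.0-fold plasma and 1.5-fold liver exposure in Child-Pugh B relative to normal hepatic function. Section 5.6 lists bilirubin increases and signs of hepatic decompensation among the observed findings.

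**Working it through.** The Protocol gives no figure to reproduce here. The check is date arithmetic on its own windows, taking 1 month = 30 days and 2 months = 61 days.

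**Inputs**
- Look-back: 2 months = 61 days (footnotes n and m, Section 7.4.1).
- Minimum step interval: 6 weeks = 42 days (Section 7.4, Appendix A).
- Post-titration sample: 1 month to 1 month + 1 week = 30 to 37 days after the step (Table 1 footnote b).
- Extension after an unscheduled up-titration: 5 more weeks = 35 days (Appendix A).
- Month 3 = Day 91; Month 6 = Day 182, window Day 168-196.
- Weekly dose after each step, Child-Pugh B: Titration 1, 5 x 2 = 10 mg; Titration 2, 10 x 2 = 20 mg; Titration 3, 5 x 7 = 35 mg.

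**Structural gap.** 61 - 42 = 19 days. A sample taken up to 19 days before one step is still in date at the earliest next step.

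**Worked path, Child-Pugh B**
1. Titration 1 at Month 3, Day 91 (to 10 mg/week).
2. Post-Titration 1 sample: 91 + 30 = Day 121 to 91 + 37 = Day 128.
3. Titration 2 at an unscheduled visit: 91 + 42 = Day 133 (to 20 mg/week), which is 5-12 days after that sample.
4. Post-Titration 2 sample: normally 133 + 30 = Day 163 to 133 + 37 = Day 170. With the extension it may be as late as 170 + 35 = Day 205, and on this path it moves to Month 6.
5. Earliest Titration 3: 133 + 42 = Day 175 (to 35 mg/week), inside the Month 6 window.
6. Age of the post-Titration 1 sample on Day 175: 175 - 128 = 47 to 175 - 121 = 54 days. It is in date.
7. It stays in date until 121 + 61 = Day 182 to 128 + 61 = Day 189.

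Titration 3 can therefore use the post-Titration 1 sample on Day 175 or at the nominal Month 6 visit, where the only sample on 20 mg/week is the one drawn that day. Without deferral, a sample on 20 mg/week would precede Day 175 by 175 - 170 = 5 to 175 - 163 = 12 days.

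**Calendar-month check.** Over 365 start dates, the sample's age at the earliest Titration 3 is 46-56 days. A sample drawn on the last day of the post-Titration 1 window is still within 2 months at nominal Month 6 for every start date, with 4-9 days to spare.

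**Does another rule close it?** The re-sampling clause in Section 7.4.1 applies when results are not available. Here a result is available and in date. Section 7.4.1 also accepts a post-titration result for titration before or at the next quarterly visit. Read literally, one post-Titration 1 sample covers both Titration 2 (before Month 6) and Titration 3 (at Month 6).

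**Other modified-regimen steps.** When Titration 1 is at a regular visit, its check cannot be deferred, so a current-dose sample should exist before Titration 2 in both Child-Pugh B and C. Nothing requires that it be the one reviewed: a sample drawn on the day of Titration 1 is only 42 days old at the earliest Titration 2.

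**The case against.** The strongest reply is that Section 7.4.1 is being read too literally. It can be taken to mean that each post-titration check supports the next step. On that reading, a deferred post-Titration 2 result counts as not available and a fresh sample is required. The reading is possible, but the text does not say it, and the footnotes permit any result within 2 months without qualification.

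The path is also narrow. It needs Child-Pugh B, an unscheduled Titration 2, use of the extension, and a prompt Titration 3. Since the post-Titration 1 sample expires on Day 182-189, Titration 2 must fall between Day 133 and 182 - 42 = Day 140 to 189 - 42 = Day 147, a slot of 7-14 days. Most subjects are expected to be on once-daily dosing. This stands, and it limits how often the gap can arise.

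On the safety stake, Section 5.5.2.2 calls the liver the primary site of action and reports no apparent effect on overall safety in Child-Pugh B/C subjects with more than 10-fold plasma exposure. Titration 3 is also half the standard maximum weekly dose (35 against 10 x 7 = 70 mg). If exposure is dose-proportional, which is an assumption, modelled liver exposure is 0.5 x 1.5 = 0.75 of that in a subject with normal hepatic function on 10 mg daily. This supports calling the gap moderate. It does not make a bilirubin rule work when it is applied to a sample from the wrong dose.

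Finally, Section 5.5.2.2 does not define tolerability as a laboratory result, and adverse event review, investigator judgement and the repeat-testing rules in Section 8.4.2.1 remain. But repeat testing needs a sample to trigger it, and on this path none is required while the subject is on 20 mg/week until the deferred visit.

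**Conclusion.** The concern holds. Followed exactly, the Protocol lets a Child-Pugh B subject go from 10 mg/week (last reviewed chemistry) through 20 to 35 mg/week, a 35 / 10 = 3.5-fold increase, with no laboratory result from the intermediate dose reviewed. The sample relied on is 47-54 days old at the earliest Titration 3 and remains usable for 7-14 days after that.

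This rests on Titration 2 taking place at an unscheduled visit 6 weeks, or little more, after Titration 1; on use of the Appendix A extension; and on the literal reading of Section 7.4.1. Outside that route the default post-titration visit supplies a current-dose sample, although nothing obliges the investigator to use it. It is a moderate weakness in a safety procedure that should be fixed. It has no bearing on the endpoint, power or type I error.

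**What to change.** In Section 7.4.1, Table 1 footnote n, Table 2 footnote m and Appendix A, require for modified-regimen subjects that the laboratory results reviewed before an up-titration were obtained after the most recent dose change, on the dose being escalated from, as well as within 2 months. In Appendix A, state that when the post-titration visit is deferred under the 5-week extension, no further up-titration may take place until its results have been reviewed.

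The cost is amendment wording in four places. The post-titration sample is already planned, so no new procedure is needed. The downside is that some Child-Pugh B/C titrations will be delayed by days to weeks, or the convenience of combining the deferred check with a titration visit will be lost.

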7.1.3. Study Duration

The study is event driven and total duration will be determined by the time required to accrue approximately 121 primary endpoint events, estimated to be approximately 8 years. Subjects are expected to have a minimum follow-up time of approximately 6 years.

7.2. Number of Subjects

It is expected that approximately 350 subjects will be randomized in the study to achieve 121 adjudicated primary endpoint events.

7.3. Planned Dosing Regimen

Subjects will be randomized to treatment with either OCA or matching placebo in a 1:1 ratio. Subjects will be dosed according to their cirrhosis status (as defined in [Section 9.7.3](#)) and applicable Child-Pugh Score (see [Section 9.7.4](#)) as outlined in Table 3.

Subjects who are non-cirrhotic or classified as Child-Pugh A at screening will receive 5 mg OCA or matching placebo once daily for 3 months. Subjects should titrate to a maximum dose of 10 mg OCA once daily (or matching placebo) at the Month 3 visit or at any study visit following the Month 3 visit based on tolerability of the product. A review of safety laboratory results (eg, chemistry, hematology, and coagulation) obtained no more than 2 months prior to the planned up-titration visit must be completed as part of the product tolerability assessment before up-titration can occur (see [Section 7.4.1](#)).

For those subjects that up-titrate to 10 mg, dose may be decreased to 5 mg at any time during the study as considered clinically appropriate (eg, tolerability). Subjects may be titrated back up to a maximum dose of 10 mg once daily based on tolerability and clinical judgment of the Investigator. A review of safety laboratory results obtained within 2 months of the planned up-titration visit date is not required prior to re-challenging a subject up to 10 mg once daily dosing, as long as the decrease in dose/dosing frequency was less than 3 months in duration.

Table 3: Planned Dosing Regimen by Cirrhosis and Child-Pugh Score

	Scheduled Dosing Regimen		
	Standard	Modified ^d	
	Non-Cirrhotic/ Child-Pugh A	Child-Pugh B	Child-Pugh C
Starting Dose ^a (Day 0)	5 mg daily	5 mg once weekly	5 mg once weekly
Titration 1 ^b (≥Month 3)	10 mg daily	5 mg twice weekly ^c	5 mg twice weekly ^c
Titration 2 ^b (≥6 weeks after Titration 1)	NA	10 mg twice weekly ^c	10 mg twice weekly ^c
Titration 3 ^b (≥6 weeks after Titration 2)	NA	5 mg daily	NA

^a Starting dose based on subject's cirrhosis status and Child-Pugh score at Screening.

^b Planned titration regimen is shown; however, the titration of dose and/or frequency is dependent on subject tolerability and/or changes in cirrhosis status or Child-Pugh score at any time during the study (see [Section 7.4](#)).

^c Dosing per the twice weekly schedule must be at least 3 days apart.

^d Refer to [Appendix A](#) for additional instructions regarding subjects following the Modified Dosing Regimen.

The dosing regimen should be determined as described in Table 4. Investigators should follow the dosing/titration schedule as shown in [Table 3](#).

Table 4: Determination of Dosing Regimen

Cirrhosis?	No	Yes	Yes	Yes
Child-Pugh Score	Any	A	B	C
Dosing Regimen	Standard		Modified for Child-Pugh B	Modified for Child-Pugh C

7.4. Dose Titration Criteria

Dose titration may follow the scheduled dosing regimens described in [Section 7.3](#) or occur due to tolerability concerns or as a result of changes in a subject's cirrhosis status (using histology or non-histological methods as defined in [Section 9.7.3](#) and [Section 9.7.4](#)) or Child-Pugh Score.

Scheduled Dose Titration - The first dose titration for any subject may occur no earlier than 3 months following initiation of OCA or matching placebo. Subsequent titrations in dose or dosing frequency for subjects following the Modified Dosing Regimens may occur no earlier than 6 weeks (via an unscheduled visit or regular visit- see [Appendix A](#)) following an up-titration.

Tolerability Dose Titration - Investigators may decrease the dosing frequency or dose for any subject at any time during the study, as considered clinically appropriate (eg, tolerability; see [Section 7.4.2](#)).

Dose Titration due to Change in Cirrhosis or Child-Pugh Score - When subjects demonstrate a change in cirrhosis status (as assessed per [Section 9.7.3](#)) or Child-Pugh Score ([Section 9.7.4](#)), dosing should be reassessed and the dosing regimen modified appropriately. Changes to the dosing regimen are not mandatory and should be based on clinical judgment as well as change in cirrhosis status. [Table 5](#) provides an overview of the possible changes in dosing regimen due to changes in cirrhosis or Child-Pugh Score. Dosing should follow the titration schedule of the new dosing regimen such that the maximum dose within that dosing regimen is ultimately attained, based on tolerability and clinical judgment.

Table 5: Changes in Dosing Regimen Due to Changes in Cirrhosis Status or Child-Pugh Score

Original Status	New Status ^a		
	Non-cirrhotic OR Child-Pugh A	Child-Pugh B	Child-Pugh C
Non-cirrhotic or Child-Pugh A	No Change	10 mg daily → 5 mg daily 5 mg daily → No change or 10 mg twice weekly ^b	5 mg or 10 mg daily → 10 mg twice weekly ^b
Child-Pugh B	5 mg daily → 10 mg daily	No Change	5 mg daily → 10 mg twice weekly ^b 10 mg twice weekly ^b → No change or 5 mg twice weekly 5 mg twice weekly ^b → No change or 5 mg once weekly
Child-Pugh C	10 mg twice weekly → 5 mg daily	10 mg twice weekly → 5 mg daily 5 mg twice weekly → No change or 10 mg twice weekly ^b 5 mg once weekly → 5 mg twice weekly	No Change

^a Once a subject begins dosing with the new dosing regimen, titration should occur as described for that dosing regimen in [Section 7.3](#) or [Appendix A](#).

^b Dosing per the twice weekly schedule must be at least 3 days apart.

Subjects who exhibit development of cirrhosis at any point in the study should be assessed per [Section 9.7.3](#). If the presence of cirrhosis is confirmed and the subject's Child-Pugh score is either B or C, the appropriate modified dosing regimen should be followed. The dose or frequency of investigational product should be down-titrated to the next lowest dosing frequency in the appropriate modified dosing regimen unless the subject is currently taking a dose and frequency also specified in the modified dosing regimen and the Investigator determines that it is clinically appropriate for the subject to continue at that dose (Appendix A).

Subjects with pre-existing cirrhosis who demonstrate a change in the Child-Pugh Score from A to B or C at any point in the study should also have their dosing modified per the appropriate dosing regimen (Appendix A).

Subjects who demonstrate an improvement in cirrhosis status or in Child-Pugh Score from B to A, or from Child-Pugh C to B, may be eligible to transition to the standard dosing regimen or the modified dosing for Child-Pugh B, respectively, based on tolerability. Prior to any dosing change, subjects must meet pre-titration assessment requirements for dosing as described in [Section 7.4.1](#).

Child-Pugh Scores will be calculated at all quarterly study visits. All associated visit data (including central laboratory results) should be entered into the eCRF in a timely fashion to confirm that the subject's Child Pugh Score has not changed. If a change in cirrhosis status (as defined in [Section 9.7.3](#)) and/or Child-Pugh Score is observed independent of a study visit, the subject should be contacted via phone to discuss the need for a dosing modification and should be asked to return to the investigative site as soon as possible if a new bottle of investigational product is required to be dispensed.

Subjects' dose and dosing frequency may be titrated up or down within the appropriate dosing regimen based on the calculated Child-Pugh Scores. Up-titration should be done per Investigator discretion and be guided by the pre-titration tolerability assessments.

